13.3.1. Planned Randomisation Methodology

Randomisation of participants will occur as described in section 6.2.

13.3.2. Planned Interim Analysis

There is no planned interim analysis of treatment effectiveness. However, an internal pilot phase was built into the trial to allow a feasibility assessment which will examine recruitment, retention and adherence. The original stop-go criteria are shown in Table 4, assessed 12 months after the first site opening. A review was held at this point, involving the TSC, DMC and funder. Recruitment was in the Red category, whilst Adherence and Retention were in the Amber category. A recovery plan was agreed, including a revised sample size (detailed in section 13.1). A further feasibility review is scheduled for month 36 of recruitment, using the same stop-go criteria. Recruitment will be measured against the overall recruitment target at month 36. Retention will be determined by return of the MENQOL-I questionnaire at 6 months and adherence will be measured by use of allocated treatment at 6 months.

Table 4: Stop-Go Criteria for the internal pilot

	Black (stop study)	Red (proceed with recovery plan)	Amber (proceed with changes)	Green (proceed)
Trial recruitment	<50%	50-79%	80-99%	≥100%
Recruitment rate relative to overall target at month 36 of recruitment (participants per month per site)	<0.35	≥0.35-0.55	0.56-0.69	≥0.70
Adherence (on allocated treatment at 6 months)	<50%	50-79%	80-99%	100%
Retention (return of MENQOL-I questionnaire at 6 months)	<50%	50-79%	80-99%	100%

The second feasibility review will be undertaken by the funder, TSC and DMC and if recruitment, retention or adherence meet the red or amber categories then additional strategies will be put in place to attempt to improve these. The review is planned to be conducted without knowledge of treatment allocation. However, the DMC will be able to access data by treatment allocation if requested.

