3.2. Trial Setting

Patients will be recruited from gynaecology clinics (specialist and generalist) in the UK. It is anticipated that around 24 sites will be required to achieve the target sample size required.

Potentially eligible patients are expected to be identified from the following routes:

Trial name:	Premature Ovarian Insufficiency Study of Effectiveness of hormonal therapy	Protocol version:	4.0	date:	01 Oct 2024	Page:	21
-------------	--	-------------------	-----	-------	-------------	-------	----

- Patients attending gynaecology clinics will be approached by a trained member of the site research team about participating in the trial.
- Clinical database searches: Hospital databases/clinic records will be searched by members of the clinical care team to identify patients ahead of their scheduled clinic appointments who have POI and who may be eligible. Patients will be sent a personalised letter offering them the opportunity to potentially take part if they are eligible, along with a copy of the Participant Information Sheet (PIS) and Informed Consent Form (ICF). The letter will include a brief introduction to the study and contact details of the local research team to find out more information and discuss the study further. The letter will also direct them to the trial website where they can find further information.
- Self-referral: Patients may make contact with the research team as a result of trial advertising and promotional material (e.g. posters, leaflets and social media).
- Peripheral hospitals may refer their patients to recruiting sites.
- Endocrinology clinics, clinical genetics and cancer centres may refer patients to the recruiting investigator within their Trust/ Board.
- Additional primary or secondary care settings may be set up as Participant Identification Centres (PICs) if required during the course of the trial. PICs will support recruitment by identifying potential research participants against the trial eligibility criteria and directing potential participants to recruitment sites.

4. Eligibility

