13.1.1. Power Calculations / sample size calculation

The original sample size was powered to detect a mean difference in lumbar spine BMD (g/cm²) of 0.05 between the HRT and the COC group at 2 years post-randomisation to ensure that the trial preserves at least the effect observed in a similar previous study¹⁷. This target difference also represented an absolute change thought to be the least significant change in spine BMD that is unlikely to be due to the precision error of the test. The precision error is best described using the smallest detectable difference, rather than the coefficient of variation, and for lumbar spine a change of BMD of at least +/-0.05g/cm² is considered clinically significant^{39,40}. Assuming that the lumbar spine BMD in each group varies with a standard deviation (SD) of 0.15, observed from 112 comparable patients in an unpublished cohort of POI women and the previous trial¹⁷, a total of 382 patients (191 per group)

Trial name:	Premature Ovarian Insufficiency Study of Effectiveness of hormonal therapy	Protocol version:	4.0	date:	01 Oct 2024	Page:	42
-------------	--	-------------------	-----	-------	-------------	-------	----

were required to detect the between-group difference of 0.05 g/cm² (a small effect size of 0.333) with a 90% power, 5% 2-sided significance level and 1:1 allocation. Attrition had been a major problem in studies of similar population, so we allowed for up to 20% loss to follow-up, requiring 480 patients to be recruited.

This sample size was expected to still have >80% power to detect a medium effect size (between-group mean difference of 0.075 g/cm², SD=0.15) between each HRT route (oral or transdermal) and the COC, assuming the proportion in one route is between 20% to 50%.

The above sample size was calculated without accounting for correlation between repeated outcome measures. At the design stage, it was decided not to account for the repeated measures design in the sample size calculation to be conservative as it was assumed that the efficiency gained by repeated measures would be offset by possible efficiency loss attributable to misspecification of any of the sample size parameters due to uncertainty about the assumptions.

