At a review after 18 months of recruitment it was recommended by the Trial Steering Committee (TSC) that the sample size should be readjusted to account for the correlation between repeated outcome measures. No outcome data was available to the TSC or investigators when the decision was made. The revised sample size uses the same parameters as the original sample size calculation but are based on a mixed-effect model analysis of repeated measures data including a baseline and two repeated post-randomisation outcome measurements, with contrasts to assess treatment effects at each time point. The calculation assumes a compound symmetry covariance structure (exchangeable), with a common variance (σ^2) for the outcome measure and a common correlation (ρ) between repeated follow-up assessments (autocorrelation). For each value of σ^2 , the required sample size increases with the correlation ρ between follow-up measures such that a correlation of 1 gives a sample size equivalent to two-sample t-test. A value of $\rho=0.4$ to 0.6 is typical in many studies. At the time of the review, there was insufficient accrued data to calculate the autocorrelation, so a conservative autocorrelation between follow-up measures of 0.6 was chosen. The sample size required for analysis to estimate the same effect as the original calculation, with 90% power, is 304. Allowing for 20% loss to follow-up requires the recruitment of 380 participants. To achieve 80% power and allowing for 20% loss of primary outcome data, 286 participants would be required.

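### The per-site recruitment bands carried over to the month-36 review do not fit 380 women in 57 months at about 24 sites, so a trial on schedule would score Red or Black

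*Protocol*

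**What the plan says.** Protocol section 13.3.2 presents Table 4 as the original stop-go criteria, applied 12 months after the first site opened. Recruitment was then Red, and the agreed recovery plan included a smaller sample size. The section continues: "A further feasibility review is scheduled for month 36 of recruitment, using the same stop-go criteria".

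Table 4 has two recruitment rows:

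- A percentage row: Black below 50%, Red 50-79%, Amber 80-99%, Green 100% or more.
- A rate row, labelled "Recruitment rate relative to overall target at month 36 of recruitment (participants per month per site": Black below 0.35, Red 0.35-0.55, Amber 0.56-0.69, Green 0.70 or more.

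The Black column is headed as the one that stops the study. On the reference point, the text says only: "Recruitment will be measured against the overall recruitment target at month 36".

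The current plan is stated elsewhere. Section 13.1.1: "Allowing for 20% loss to follow-up requires the recruitment of 380 participants". Section 3.2: "It is anticipated that around 24 sites will be required to achieve the target sample size required". The Trial Summary gives an expected recruitment duration of 57 months. The protocol gives no planned per-site rate and no site-opening schedule, and it does not say which recruitment row prevails if the two disagree.

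**The concern.** The rate row is the percentage row in other units: 0.35/0.70 = 50% and 0.56/0.70 = 80%. The table therefore treats 0.70 women per site per month as fully on plan. The current target, duration and site count imply a much lower rate. A trial recruiting exactly as planned would then be reported to the funder, TSC and DMC as failing, possibly in the band labelled as stopping the study. The percentage row does not settle the matter, because its denominator at month 36 can be read in two ways.

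**Working it through.** **Inputs.** Target 380 and number for analysis 304 (section 13.1.1); 57 months (Trial Summary); about 24 sites (section 3.2); band limits 0.35, 0.56 and 0.70 (Table 4).

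**1. The target reproduces.** With difference 0.05, SD 0.15, 90% power, 5% two-sided and correlation 0.6, the number per arm is 2 × (0.15 × (1.960 + 1.282)/0.05)² × (1 + 0.6)/2 = 151.3. This rounds up to 152 per arm, or 304 in total, and 304/0.80 = 380. Both figures agree with the protocol, so the numerator of the planned rate is sound.

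**2. On-plan rate with all 24 sites open throughout.** 380/57 = 6.67 women per month, and 6.67/24 = 0.278 per site. Linear accrual gives 36 × 6.67 = 240 women by month 36, and 240/(36 × 24) = 0.278 again. This is below 0.35 (Black) and is 0.278/0.70 = 40% of the Green rate.

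**3. What the bands would demand of 24 open sites by month 36.**

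- To leave Black: 0.35 × 24 × 36 = 302 women.
- To reach Green: 0.70 × 24 × 36 = 605 women, more than the whole target.
- Enrolling all 380 by month 36, which is 21 months early: 380/(36 × 24) = 0.44, still Red.

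**4. Dependence on the average number of open sites.** At 6.67 women per month, the rate reaches 0.35 at 6.67/0.35 = 19.0 sites, 0.56 at 6.67/0.56 = 11.9 sites and 0.70 at 6.67/0.70 = 9.5 sites. Black therefore applies above about 19 open sites on average, Red between about 12 and 19, and Green only at about 9.5 or fewer.

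**5. Gradual opening (my assumption, since no schedule is given).** Suppose the 24 sites open linearly over R months. Site-months are then 24 × (57 − R/2) over the full period and 24 × (36 − R/2) by month 36. Two accrual patterns that both reach 380 on time give:

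| R (months) | Constant per-site rate: 380/[24(57 − R/2)] | Linear accrual: 240/[24(36 − R/2)] |
|---|---|---|
| 0 | 380/1368 = 0.278, Black | 240/864 = 0.278, Black |
| 12 | 380/1224 = 0.310, Black | 240/720 = 0.333, Black |
| 18 | 380/1152 = 0.330, Black | 240/648 = 0.370, Red |
| 24 | 380/1080 = 0.352, Red | 240/576 = 0.417, Red |
| 36 | 380/936 = 0.406, Red | 240/432 = 0.556, Red/Amber edge |

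The change from Black to Red comes at R of about 24 months in the first column and about 15 months in the second.

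**6. The percentage row.** The 240 women at month 36 are 240/380 = 63% of the full target (Red), or 240/240 = 100% of the number due by then (Green).

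**The case against.** The strongest reply is that 24 is a total, not the number of sites open from the first month. Sites open in stages, so 0.278 is a lower bound on the planned per-site rate. That is right. It rules out the reading that an on-schedule trial is bound to score Black. It does not rescue the row: in the schedules above, staggering moves the result to Red, at best to the Red/Amber edge, and never to Green.

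A second reply is that the review rests on judgement. The text on the second review prescribes action only for red or amber, the stop consequence appears only in the column header, and Red at the first review led to a recovery plan. This stands as a limit on the practical consequence. A reader might infer that Table 4 is the only formal route to stopping the trial. Sections 14.4 and 14.5 do not support that: the TSC decides on stopping for safety or efficacy, and the DMC advises on whether recruitment should continue.

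A reader might also infer that 0.70 was derived from the earlier target of 480. The protocol states neither the duration nor the site count behind the original bands, so their origin cannot be recovered. The row label already mentions month 36, so it may have been partly edited. What the text does establish is that the criteria are called original and are to be used unchanged.

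Finally, measuring against the target at month 36 can naturally mean the number due by then. That reading is reasonable but is not the only one. The fair complaint is one ambiguous row beside a rate row that may disagree with it, not three separate verdicts.

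**Conclusion.** The point holds. On the protocol's own target, duration and site count, the rate row grades an on-schedule trial Black (0.278) if all 24 sites are open throughout. It grades it Red (about 0.35 to 0.42) if they open linearly over 24 months. Green would need an average of about 9.5 or fewer open sites, against about 24 anticipated. The split between Red and Black depends on an opening schedule that the protocol does not give, and the table above covers linear opening over up to 36 months only. The uncertainty over the percentage denominator and the governing row does not depend on that schedule. The error affects a feasibility decision. It does not touch the primary analysis or the type I error.

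**What to change.** Before the month-36 review, do one of the following:

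- **Re-derive the rate row.** Set Green, Amber and Red to start at 100%, 80% and 50% of 380 divided by the planned site-months, with Black below. The limits are 0.28/0.22/0.14 only if all 24 sites are open for all 57 months. With linear opening over 24 months and a constant per-site rate, 380/1080 gives 0.35/0.28/0.18. The opening plan must be fixed first: a Green limit of 0.28 applied to 1080 site-months would pass 0.28 × 1080 = 302 women, 79% of the target.
- **Drop the rate row.** Judge recruitment by the percentage of the target due by month 36, which is 240 if accrual is planned as linear.

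In either case, state which denominator the percentage row uses and, if both rows stay, which one governs. The cost is one table edit agreed with the funder, TSC and DMC, with no effect on participants.

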13.3.3. Planned Final Analyses

Analysis of the primary outcome and secondary outcomes up to 2 years will be performed after all data up to the 2 year point has been collected and cleaned and the SAP finalised.

Analysis of the secondary outcomes between 3 and 5 years will be performed after all data up to the 5 year point has been collected and cleaned.

13.3.4. Planned Subgroup Analyses

Subgroup analyses for the primary outcome will be performed according to age at randomisation (≥18- <25 years or ≥25 - <40 years)), BMI (<25 kg/m² or 25 - <30 kg/m² or ≥30 kg/m²), hysterectomy (yes or no), smoking status (quit smoking/never smoked or current smoker), and previous oestrogen

Trial name:	Premature Ovarian Insufficiency Study of Effectiveness of hormonal therapy	Protocol version:	4.0	date:	01 Oct 2024	Page:	45
-------------	--	-------------------	-----	-------	-------------	-------	----

treatment (Yes or No), by including appropriate interaction terms in the mixed effect model. The trial is not powered to detect any interactions hence the subgroup analyses will be treated as exploratory.

14. Trial Organisational Structure

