After informed consent (and if required a washout period), baseline data will be collected by a member of the site research team and the participant will be enrolled using the online trial randomisation system. All participants are required to have had a DEXA bone density measurement of lumbar spine and hip in the 6 months prior to randomisation. Further information on baseline data collection requirements is detailed in Section 8.2.

An authorised member of the site research team will then log into the secure randomisation system and randomise the participant.

6.2.Randomisation

Eligible women will be individually randomised on a 1:1 ratio to one of the treatment groups using an online randomisation system developed and maintained by the NCTU. Access to the system will be granted by the NCTU in accordance with the roles delegated by the Principal Investigator on the Site Delegation Log.

Treatment will be assigned using a minimisation algorithm balancing on the following factors:

- Recruiting site
- Age at randomisation (≥ 18 - < 25 years or ≥ 25 - < 40 years)
- Body mass index (< 25 kg/m² or 25 - < 30 kg/m² or ≥ 30 kg/m²)
- Smoking status (quit smoking/never smoked or current smoker)
- Previous oestrogen treatment (Yes or No)

The minimisation algorithm will include a probabilistic element to allocation, making prediction of the allocated group virtually impossible.

For women randomised to HRT, participant preference will be taken into account when deciding which route of administration, oral or transdermal, to be used. Where there is no preference, the route will be randomly selected using an online randomisation system.

Trial name:	Premature Ovarian Insufficiency Study of Effectiveness of hormonal therapy	Protocol version:	4.0	date:	01 Oct 2024	Page:	25
-------------	--	-------------------	-----	-------	-------------	-------	----

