13.3. Analysis of Outcome Measures

The analysis and reporting of the trial will be in accordance with CONSORT guidelines. A full statistical analysis plan (SAP) will be developed and agreed prior to database lock for the analysis of the primary outcome at 2 years.

Trial name:	Premature Ovarian Insufficiency Study of Effectiveness of hormonal therapy	Protocol version:	4.0	date:	01 Oct 2024	Page:	43
-------------	--	-------------------	-----	-------	-------------	-------	----

Appropriate descriptive statistics (mean, standard deviation, median, lower and upper quartiles, minimum, maximum or frequencies and percentages) for the demographic and clinical outcome measures at baseline will be used to assess balance between the randomised arms at baseline, but no formal statistical comparisons will be performed. Baseline characteristics will also be descriptively compared between those randomised and those analysed to see if the attrition has introduced any imbalances. Descriptive statistics appropriate for the outcome will also be presented for all outcomes at all collected time points by treatment group.

The primary comparative analysis will be based on intention-to-treat, analysing participants in the groups to which they were randomised. The evaluation of the primary outcome of BMD in the lumbar spine at 2 years will be performed using a mixed effects model to allow for all available follow-up data (1 year, 2 year) to be used, adjusted for the baseline BMD in the lumbar spine and the minimisation variables as fixed effects except site which will be entered as a random effect. The model will include a treatment by time interaction to obtain the estimates of treatment effect at each follow-up time, with 2 years being the primary evaluation. An interaction between each covariate and time will be added to get a different adjustment for each covariate at each time point. The estimated between group effect will be presented using the difference in means, with a 95% confidence interval. The primary treatment comparison will be the contrast between allocated treatment groups at 2 years.

Sensitivity analyses for the primary outcome will include:

- Complete case analysis based on observed outcome data at 2 years
- Use of multiple imputation with auxiliary variables (if applicable) not included in the primary analysis also included in the imputation model.

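### Section 13.3.4 tests age and BMI effect modification on the minimisation bands only, with one age band from 25 to <40; a continuous interaction should be pre-specified beside them

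*Protocol*

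**What the plan says.** Protocol section 13.3.4 begins: "Subgroup analyses for the primary outcome will be performed according to age at randomisation". It defines the primary-outcome subgroups by "age at randomisation (≥18- <25 years or ≥25 - <40 years") and "BMI (<25 kg/m² or 25 - <30 kg/m² or ≥30 kg/m²"), together with hysterectomy, smoking and previous oestrogen treatment. Each is examined through an interaction term in the mixed model. The section says that the trial lacks power for interactions and labels these analyses exploratory.

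The bands match the minimisation factors in section 6.2: "Age at randomisation (≥ 18 - < 25 years or ≥ 25 - < 40 years") and "Body mass index (< 25 kg/m² or 25 - < 30 kg/m² or ≥ 30 kg/m²"). No interaction with age or BMI on its measured scale is mentioned anywhere in the protocol.

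For the primary model, section 13.3 says that the analysis is "adjusted for the baseline BMD in the lumbar spine and the minimisation variables as fixed effects except site", with site random and each covariate interacting with time. It does not say whether age and BMI enter that model as bands or as measured values.

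**The concern.** A minimisation algorithm needs categories; an interaction test does not. With these bands, women of 25 and 39 count as alike and women of 24 and 25 as different. Section 1.2.1 gives reasons for the eligibility limits of 18 and 40, but the protocol gives no analytic reason for a cut at 25.

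Eligibility and minimisation require age, and the baseline assessments include height and weight, so the finer information is already collected. Section 13.3.4 concedes that the interaction tests are weak. Banding may weaken the age test considerably further, and a real trend of treatment effect with age could be missed.

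**Working it through.** **Inputs from the protocol.** Eligible ages are 18 to <40 (section 4.1), with the age cut at 25 and BMI cuts at 25 and 30 (sections 6.2 and 13.3.4). SD is 0.15 g/cm², target difference 0.05, power 90%, two-sided 5% and 1:1 allocation (section 13.1.1). The correlation between follow-up measures is 0.6, with 304 analysed and 380 recruited (same section).

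**Assumed.** The age and BMI distributions (none is given), and an interaction linear in age unless stated otherwise.

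**Step 1: the plan's own figure.** The protocol has no figure for age information. Its sample size does reproduce. Per arm, 2 × (1.960 + 1.282)² × (0.15/0.05)² ≈ 189.1. Multiplying by (1 + 0.6)/2 = 0.8 gives 151.3, rounded up to 152, so 304 in total, and 304/0.8 = 380. N = 304 is used in step 4.

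**Step 2: information kept by the age split.** For a linear effect, the share kept is r² = p(1 − p)(m₂ − m₁)² / Var(age). Here p is the proportion under 25, and m₁ and m₂ are the band means.

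- Uniform over 18–40: p = 7/22, m₂ − m₁ = 32.5 − 21.5 = 11, Var = 22²/12 = 40.33. So r² = (7 × 15/22²) × 121/40.33 = 26.25/40.33 = 0.65, a loss of 35%.
- Normal with mean 33 and SD 5, truncated to 18–40: p = 0.058, m₁ = 23.0, m₂ = 32.8, Var = 18.3. So r² = 0.058 × 0.942 × 9.74²/18.3 = 0.28, a loss of 72%.

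| Assumed ages (before truncation) | Under 25 | Kept | Lost |
|---|---|---|---|
| Uniform 18–40 | 32% | 0.65 | 35% |
| Normal 29/6 | 23% | 0.54 | 46% |
| Normal 31/5.5 | 14% | 0.44 | 56% |
| Normal 33/5 | 6% | 0.28 | 72% |
| Normal 34/5 | 4% | 0.23 | 77% |

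These rows are not bounds. With half of the women under 25 and ages uniform within each band, the loss is 27%. Fewer women under 25 than in the last row would push it above 77%.

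**Step 3: power, holding the banded test at 30%.** A power of 30% corresponds to a noncentrality of 1.436. Linear-test power is Φ(1.436/√r² − 1.96).

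| r² | Linear continuous test | Flexible test, 3 df | Linear test if the effect truly steps at 25 |
|---|---|---|---|
| 0.65 | 43% | 29% | 21% |
| 0.44 | 58% | 41% | 16% |
| 0.28 | 77% | 61% | 12% |

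The third column uses a noncentral chi-square with noncentrality (1.436/√r²)². The last column uses Φ(1.436·√r² − 1.96). Because banded power is held at 30%, each row implies a different underlying effect. The rows are not a range for one effect.

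**Step 4: one fixed effect.** Suppose the treatment difference changes by 0.10 g/cm² per 10 years of age, with N = 304 and SD 0.15. The noncentrality is 0.01 × SD(age) × √304/(2 × 0.15), multiplied by √r² for the banded test.

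- Uniform ages (SD 6.35): 3.69 continuous against 2.98 banded, so 96% against 85% power.
- Normal 33/5 (SD after truncation 4.3): 2.49 against 1.33, so 70% against 26%.

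**Step 5: BMI.** Three bands lose 18–22% for assumed means of 25–27 and SDs of 4.5–6 kg/m².

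**Step 6: the primary model, if age were banded there.** The inflation in sample size is (1 − R²·(1 − loss))/(1 − R²), where R² is the residual outcome variance that age explains after baseline BMD. For an assumed R² of 1–5% and losses of 35–73%, it is 1.0035 to 1.038, about 0.4–4%.

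**The case against.** **Shape.** The gain depends on a roughly linear effect, and the protocol supports no particular shape. If the effect steps at 25, the banded test is the right one and the linear test is weaker (step 3). A 3-df flexible test gains nothing with uniform ages: 29% against 30%. This stands, and it is why the continuous test should sit beside the bands and not replace them.

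**Usefulness of bands.** Pre-specified bands that match the minimisation strata give estimates clinicians can read, and they leave no cut-point to choose afterwards. This also stands. The SAP may add a continuous test; even so, section 13.3.4 states the bands as the analysis, so this is a choice the protocol makes and not a detail left open.

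**Consequence.** The subgroups are exploratory, and no bias or type I error problem follows. This stands and keeps the priority low.

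**Two stronger readings are tempting.** A reader might infer that the primary adjustment also uses only the bands, because section 13.3 takes in "the minimisation variables as fixed effects except site which will be entered as a random effect" and section 6.2 defines those variables as bands. Section 13.3 does not state the coding, which is ordinary SAP content, so the inference is not established. A reader might also take a loss of a third to three quarters as a fact about this trial. It is not, because the protocol gives no age distribution.

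**Conclusion.** The point holds for the subgroup tests. Section 13.3.4 fixes age and BMI effect modification on the minimisation bands alone. Under a roughly linear age effect, the split at 25 loses about 35% of the age information with uniform ages and about 72% with some 6% of women under 25, both on assumed distributions. The BMI loss is about a fifth on similar terms.

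This is a minor improvement to an exploratory analysis. The randomised comparison is unbiased and the sample size of 304/380 is unaffected. In the primary adjustment, continuous age would be a small gain (step 6) and not the correction of an error.

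**What to change.** In section 13.3.4, pre-specify treatment-by-age and treatment-by-BMI interactions with both variables continuous, in the same mixed model. Add a non-linearity check, such as a quadratic or spline term. Keep the band-specific estimates alongside and label everything exploratory. Settle this before the 2-year database lock, by which time section 13.3 already requires the SAP to be agreed; added later, the test would be post hoc.

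Optionally, state in section 13.3 or the SAP how age and BMI are coded in the adjustment, with continuous terms preferred.

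The change is wording only: no new data, no change to randomisation and no change to the sample size. Its price is an assumed shape for the effect and one more exploratory test per factor.
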